MATEC affiliated clinics in the Midwest region are eligible to participate in Aim 1 if meeting these criteria: (1) Clinic must have at minimum 40 current patients who are: racial/ethnic minority AND have a 'detectable' viral load AND are aged 16-35 years; (2) clinic must be willing to commit at least one staff person as lead for registering clients to receive the intervention, completing consent, and administering research surveys; (3) clinic must be willing to provide deidentified individual-level data for registered TXTXT participants, including viral load, retention in care (dates of clinic visits) at least twice per year; (4) clinic must not be using a competing medication reminder text messaging system; (5) clinic must be willing and able to rely on Lurie IRB. Once sites sign a memorandum of commitment, the study coordinator will schedule a conference call to conduct a standard of care questionnaire (Appendix K). The standard of care questionnaire will document existing clinic approaches to support adherence as well as any ancillary services (e.g., transportation assistance). This information will form a descriptive profile for each clinic.

Study Inclusion

For inclusion in the TXTXT intervention individuals must meet the following criteria: 1) diagnosed with HIV-infection and on ART regimen for at least one month (not new to ART); 2) aged 16-35 years; 3) have a viral load ≥ 200 c/mL and/or report poor adherence (<90% of pills taken in the last 30 days); 4) able to receive text messages; 5) provide informed consent for research component; and 6) are a patient of a participating clinic

Study Exclusion

Exclusion criteria includes: 1) those who are unable to give informed consent 2) those who are participating in other studies that impact primary and secondary outcomes.

Procedures for Recruitment and Informed Consent

Aim 1: Youth living with HIV (aged 16-35 years) who meet study inclusion criteria will be recruited by study staff from participating clinics. The EMR will identify potentially eligible patients who will be invited to complete further study screening and enrollment.

We will ask each clinic to construct a list of eligible patients and carefully track outreach, screening, and enrollment on an enrollment log provided. Clinics may enroll up to 50 participants (to account for 20% attrition, final sample of 40 participants per clinic).

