In order to assess feasibility, acceptability and satisfaction of the intervention we will use descriptive statistics using a combination of objective (e.g., rates of participation, intervention completion) and subjective measures (e.g., reported satisfaction, acceptability). In order to characterize adherence and retention in care throughout the course of the study, Kaplan-Meier survival curves will be used to measure time to adherence and retention, and Cox proportional hazard ratios will be used to assess whether individual-level factors are associated with shorter mean time to outcome. To measure reach of the intended participants, we will compare the study sample to those available in the sampling frame (proportion of those enrolled to those eligible). To measure adoption of clinic partners, we will evaluate the number of clinic partners who propose to continue with text messaging as adherence support post study (proportion of clinics who propose to continue TXTXT post study to total clinics). Satisfaction and acceptability will be measured by standard quantitative scales, summary total scores will be evaluated to determine whether or not ≥90% ratings were achieved.

Outcome definitions

Medication adherence: greater than or equal to 90% on self-reported visual analog scaler (non-adherence categorized at less than 90%)

Retention in care³³: two visits 90 days apart in the past year will be considered retained in HIV care

Viral suppression³⁴: VL < 200 copies/mL will be considered virally suppressed

Sample size, power calculation, and clinic scale up

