The Midwest AIDS Training and Education Center (MATEC) is the ideal partner and stakeholder for us to carry out the proposed project. The partnership with MATEC will not only ensure the feasibility of this project but will also serve as a valuable partner in future work to increase dissemination of effective interventions throughout the Midwest and via strategic connections to the larger AETC network. MATEC has a 32-year history as an AETC covering 7 jurisdictions across a 10-state region and oversees 8 different federally funded projects in the Midwest. Further, MATEC leads a practice transformation cohort consisting of 13 Ryan White funded clinics with the goal of advancing plans to End the Epidemic by increasing testing, identification of PWH, linkage to and retention in HIV care, and increasing viral suppression. We sought collaboration with MATEC specifically for this project because they are a regional hub for capacity development among HIV/AIDS service providers in the Midwest.

Study Population

Poorly adherent racial/ethnic minority youth living with HIV aged 16-35 years inclusive of all gender and sexual identities and orientations, including young gay, bisexual and other MSM, young cisgender women and young transgender women across multiple clinic sites in the Midwest US. Staff at the clinic sites will be asked to give feedback on the implementation of the EBI. Staff must be 18 years or older, currently employed at the clinic site, have participated in the implementation of the EBI, and speak and understand English.

Inclusion and Exclusion Criteria

Study Inclusion

CFIR Participant Feedback

To provide feedback on the intervention, individuals must meet the following criteria: 1) 16-35 years old;

2) current HIV care patient of clinic site; 3) HIV positive as identified by the EMR; 4) speak and understand English; 5) have aviral load >200c/mL; and 6) participated in the TXTXT intervention.

CFIR Staff Feedback

Staff are eligible to provide feedback if they are: 1) 18 years of age or older; 2) currently employed at the clinic site; 3) have participated in the implementation of the TXTXT; 4) speak and understand English.

Study Exclusion

Exclusion criteria includes: 1) those who are unable to give informed consent; and 2) those who are participating in other studies that impact primary and secondary outcomes.

Procedures for Recruitment and Informed Consent

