Youth participants and clinic staff will be recruited to participate in implementation science surveys and interviews; youth participants will be referred to investigators from participating clinic staff; [name] and [name] will identify potential staff participants.

When potential participants are interested in enrolling in the study (Aim 2), members of the research team will conduct eligibility assessment and consent conferences with participants (Appendix K). Participants who are aged 16-17 years will complete informed assent; a waiver of parental consent will be obtained. Lurie Children's IRB will ensure that the assent/consent forms meet institutional and funding source standards. Lurie Children's requires that research participants review and sign an informed assent/consent form. The informed assent/consent forms include information about the overall purpose of the study, study procedures, potential risks, potential benefits to participating for individuals and society, alternatives to participating in the study, confidentiality of data, incentive for participation (\$40), and contact information for the site's Principal Investigator and the IRB (appendix K). Once informed consent has been obtained, the clinic staff will have the form reviewed by a fellow team member, who will confirm that it is fully completed before it is filed in a secure location under double-lock when not in use and with restricted access during work hours and/or when unattended.

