research will be disclosed to others without their written permission, except if necessary to protect their rights or welfare (for example, if they are injured and need emergency care) or if required by law (i.e., child or elder abuse, harm to self or others).

Retention

Aim 2 participation is a single point in time, and therefore retention metrics will not be tracked.

Sampling

Feedback will be collected from up to 60 participants. The study coordinator based at MATEC will work with participating clinics to randomly select 4-5 participants from their enrollment log. Potential participants will be invited to participate in this additional interview (Appendix H & I). Participating individuals will complete a short open-ended questionnaire that collects information regarding the CFIR constructs (Appendix J).³⁷ The interview will last up to 30 minutes. Feedback will also be collected from up to 24 clinic staff at participating sites (1-2 staff per clinic). Staff are eligible to provide feedback if they are:1) 18 years of age or older; 2) currently employed at the clinic site; 3) speak and understand English. Clinic staff will be interviewed by the study coordinator or [name] to determine what barriers and facilitators existed at each site that may have impacted the intervention. The interview will focus on the CFIR dimensions of inner setting, outer setting, intervention characteristics, individual characteristics, and process of implementation (Appendix J). The interview will last up to 60 minutes.

Data Analysis Plan and Variables

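### The Aim 2 participant interviews require an undated viral load above 200 c/mL, so on either reading they exclude a group that the trial enrols, and the interviewees cannot represent the enrolment log

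*Combined protocol and SAP*

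**What the plan says.** The participant criteria are in Aim 2, Study Inclusion, CFIR Participant Feedback. They open with "To provide feedback on the intervention, individuals must meet the following criteria", so all six are mandatory. The fifth and sixth are that the person "have aviral load >200c/mL; and 6) participated in the TXTXT intervention". No date or time window is attached to the viral load.

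Four other places bear on this:

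- **Aim 2, Procedures for Recruitment and Informed Consent.** Once a person is interested in Aim 2, "members of the research team will conduct eligibility assessment and consent conferences with participants".
- **Aim 2, Sampling.** Clinics are to "randomly select 4-5 participants from their enrollment log", and "Feedback will be collected from up to 60 participants". No viral load restriction appears here.
- **Aim 1, Study Inclusion.** People may enter the trial if they "have a viral load ≥ 200 c/mL and/or report poor adherence". The Aim 1 Sampling section tells clinics to contact suppressed patients and ask about their adherence.
- **Outcome definitions.** "VL < 200 copies/mL will be considered virally suppressed". Suppression and self-reported adherence of at least 90% are separate primary outcomes.

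**The concern.** Aim 2 asks what helped and what hindered TXTXT. The participant interview guide asks whether the intervention was effective, what benefit the person got from it, whether they recommended it to others, and whether the clinic should keep it a priority. Those answers are likely to differ between people whose virus is controlled and people whose virus is not.

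A criterion that requires an unsuppressed viral load in people who have already taken part removes one side of that contrast. The plan intends to tabulate interview codes by participant descriptors. On the time-of-interview reading, no comparison of suppressed with unsuppressed participants would be possible. The dissemination section then uses study data to identify what would ease or impede the integration of TXTXT into clinics, so a one-sided sample could carry through to the study's practical product. Each participant is interviewed at a single point in time, so the missing views would be hard to recover later.

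**Working it through.** **Step 1: reproduce the plan's own figure.** There are 12 clinics, with 4 to 5 participants drawn at each: 12 × 4 = 48 and 12 × 5 = 60. The upper value matches the stated maximum of 60.

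**Step 2: compare the thresholds.** The interview criterion is a viral load above 200. Suppression is a viral load below 200. The two sets do not overlap, so nobody who is suppressed on the date to which the criterion refers can be interviewed.

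**Step 3: apply both possible dates.**

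| Viral load read at | Excluded | Still eligible, subject to the other criteria |
|---|---|---|
| Interview | Everyone then suppressed: those who became suppressed on TXTXT, and those who entered suppressed and remain so | Those then above 200 |
| Trial entry | Those enrolled while suppressed, on poor adherence alone | Those above 200 at entry, including any who later became suppressed |

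The present tense, the pairing with completed participation and the eligibility check at Aim 2 recruitment favour the first row, but nothing in the text settles it. Neither row leaves the whole enrolment log eligible.

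**Step 4: size, on the time-of-interview reading.** Let s be the share suppressed at interview. The expected number eligible from a draw of n is n × (1 − s). The documents give no value for s, so a wide range is assumed.

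| Assumed s | Eligible from 60 | Eligible from 48 | Ineligible among the 480 expected for analysis (480 × s) |
|---|---|---|---|
| 20% | 48 | 38.4 | 96 |
| 40% | 36 | 28.8 | 192 |
| 60% | 24 | 19.2 | 288 |
| 70% | 18 | 14.4 | 336 |

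These counts assume that people found ineligible are not replaced. Further draws could restore the number of interviews but not their make-up: on this reading, none of the interviewees is suppressed, whatever the value of s.

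**Step 5: size, on the entry reading.** The same formula applies, with s replaced by the share enrolled while suppressed. The documents do not give that share either.

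The control proportions in the power table (25%, 35%, 45% and 55%) are not a substitute for s. They are assumed adherence in the control group, not suppression among people who received TXTXT.

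**The case against.** The best defence is that the criterion was carried over from trial entry. Age, being a clinic patient, HIV status and viral load all echo the Aim 1 criteria. The Aim 1 Sampling section describes viremic patients with the same above-200 threshold, and the Aim 2 study population repeats the Aim 1 text. This reading is plausible. It means that the exclusion of people who became suppressed on TXTXT cannot be stated as fact. It does not rescue the criterion, because people enrolled while suppressed are then still barred.

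Three stronger readings are tempting, and the documents do not support them.

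- **That the interviews reach only non-responders.** Adherence is a separate primary outcome and the one used for the power calculation. Someone above 200 may have reached 90% adherence. The group is virologically unsuppressed, not necessarily non-adherent.
- **That the random draw flatly contradicts the criterion.** Drawing names from a log and then screening them is an ordinary sequence. The Sampling section is also not a full eligibility list: its staff criteria omit one that the inclusion section requires. The fault is that screening leaves a sample that no longer represents the log.
- **That the findings are biased downward by a known amount.** The interviews are coded by directed content analysis and estimate no effect. A less favourable picture is a reasonable expectation, not a calculated result.

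It also stands that other sources fill part of the gap. The online survey goes to both arms at baseline, 3 and 6 months without a viral load filter. It covers barriers, facilitators, acceptability and satisfaction, and asks openly what worked best. Up to 24 clinic staff are interviewed as well. None of this replaces the in-depth participant account that Aim 2 sets out to collect.

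**Conclusion.** The point holds in a limited form. The criterion is undated, and each possible date excludes a group that the trial enrols: everyone suppressed at interview, or everyone suppressed at entry. In either case the interviewees do not represent the log from which they are drawn, and the plan gives no reason for the restriction.

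The share lost cannot be derived from the documents. The fall from 60 drawn to between 48 and 18 eligible rests on an assumed 20% to 70% suppressed, on the time-of-interview reading, and on no replacement of ineligible people. That no suppressed participant would be interviewed on that reading needs no assumption.

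The consequence is confined to the qualitative participant interviews.

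**What to change.** Delete the viral load criterion from the Aim 2 participant list, so that anyone in the enrolment log who received TXTXT and meets the other criteria can be drawn. Make Aim 1 Study Inclusion, the Aim 2 participant criteria and Aim 2 Sampling agree. In Sampling, state that the draw is from all such participants and whether people found ineligible are replaced.

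If the authors have a reason to keep a viral load criterion, they should state the reason and the date of the measurement, and describe the interviews as covering that subgroup only. Dating the criterion would remove the ambiguity but not the selection.

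Stratifying the 4 to 5 interviews per clinic by suppression status is optional. It could use the 6-month medical record data already planned, provided the interviews follow that extraction.

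The cost is one deleted line and a sentence or two in Sampling. No extra interviews or data collection are needed, but the change has to be made before interviewing starts.

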APPENDIX A: TXTXT Intervention Description

COMPENDIUM OF EVIDENCE-BASED INTERVENTIONS AND BEST PRACTICES FOR HIV PREVENTION

TEXT MESSAGING INTERVENTION TO IMPROVE ANTIRETROVIRAL ADHERENCE AMONG HIV-POSITIVE YOUTH (TXTXT)

Good Evidence – Medication Adherence

INTERVENTION DESCRIPTION

Target Population

- HIV-positive adolescents and young adults with poor medication adherence

Goals of Intervention

- Improve adherence to antiretroviral therapy

Brief Description

Text Messaging Intervention to Improve Antiretroviral Adherence among HIV-Positive Youth (TXTXT) is an individual-level intervention for HIV-positive adolescents and young adults with poor medication adherence. The intervention consisted of daily youth-friendly 2-way text messages delivered over 6 months. Text messages were used to remind participants to take their medication and confirm that the medication was taken. Intervention participants tailored and personalized text message reminders to their medication regimen, including the number and time of dosages. Text message reminders and follow-up messages were also personalized to reflect content meaningful to their culture or other sources of identity. To protect confidentiality, intervention participants were encouraged to delete messages after taking medication, use messages that would not reveal their HIV status or mention medication, and received information about phone confidentiality (e.g., passcode protection). Message delivery was timed to coincide with the participant's dosing schedule. Youth-friendly motivational or encouraging follow-up messages were delivered that were based on the youth's responses to taking their medication (e.g., "Well done!" or "You can do it!"). All text messages were sent to participants' personal cell phones.

Theoretical Basis

- Social Cognitive Theory

Intervention Duration

- Daily text message reminders delivered over 6 months

Intervention Setting

- Anywhere participants had access to their cell phone

Deliverer

- Text messages delivered by Remedy Health Media

MEDICATION ADHERENCE (MA) CHAPTER – TXTXT

Last updated November 4, 2016

Appendix B Training Material

TXTEXT CommCare Platform Training

Brothers Health Collective

The Potocsnak Family Division of
Adolescent and Young Adult Medicine

November 12th, 2019

Fundamentals

What is Dimagi and CommCare?

1. Dimagi is a software technology company that designs clinical interfaces and health information systems

[figure not shown]
- 2.

- 3.

[figure not shown]
What does the TXTXT App do?

1. receive a message
2. receive a message 15m later
3. receive a message

1. client: Slay the day
2. Did you slay the day?! 1:Yes, 2:No.
3. I'm so glad to hear that! Hurray!

order and question text
daily texts
weekly text

Two User Roles

Two User Roles: App User and Admin

Mobile Worker: The TXTXT App

1. App User
2. Register a case (i.e., client/participant) to they can start receiving text messages
3. Revise text message preferences for a previously registered case

Web User: CommCareHQ

4. Admin
5. Monitor text message history for all cases
6. Download aggregate text message data
7. Manage Mobile Workers and Web Users
8. Managing the system and users

Two User Roles: App User and Admin

Mobile Worker: The TXTXT App

9. App User

10. Register a case (i.e., client/participant) to they can start receiving text messages
11. Revise text message preferences for a previously registered case
12. Anyone who will register clients into the system to receive messages will need a Mobile Worker account

Web User: CommCareHQ

13. Admin
14. Monitor text message history for all cases
15. Download aggregate text messagedata
16. Manage Mobile Workers and Web Users
17. Managing the system and users
18. Only the few people who will monitor study progress, run data queries, and manage users need a Web User account

Two User Roles: App User and Admin

Mobile Worker: The TXTXT App

19. App User
20. Register a case (i.e., client/participant) so they can start receiving text messages
21. Revise text message preferences for a previously registered case
22. Anyone who will register clients into the system to receive messages will need a Mobile Worker account

Anything other than registering a client or updating a client's preferences requires a Web User account

Web User: CommCareHQ

1. Admin
2. Monitor text message history for all cases
3. Download aggregate text messagedata
4. Manage Mobile Workers and Web Users
5. Managing the system and users
- 6. Only the few people who will monitor study progress, run data queries, and manage users need a Web User account**

[figure not shown]
Two User Roles: App User and Admin

You log in as a Mobile Worker and Web User using the same landing page, but with different credentials

1. Mobile Worker

1. Username: created for you by Web User
2. Password: created for you by Web User

Logs into TXTXT App

[figure not shown]

1. Web User

[figure not shown]
1. Username: Email
2. Password: you set it up after you are invited via email to be a WebUser

Logs into CommCareHQ

[figure not shown]
Two User Roles: TXTXT App as a Mobile Worker

[figure not shown]
Two User Roles: TXTXT App as a Mobile Worker

Two User Roles: CommCare HQ as a Web User

Two User Roles: CommCare HQ as a Web User

The screenshot shows the CommCare HQ web interface. At the top, a navigation bar includes links for Dashboard, Reports, Data, Users, Applications, Web Apps, and Messaging. A sub-navigation bar for the 'Lurie Children's Hospital' project is also visible. The main content area is titled 'Welcome Back to CommCare HQ' and features a grid of eight cards representing different project components:

- Applications:** Shows a mobile phone icon and the text 'TXTXT for ART Adherence'.
- Reports:** Shows a line graph icon.
- Data:** Shows a bar chart icon and the text 'participant (created 2019-02-01)'.
- Users:** Shows a user profile icon.
- Messaging:** Shows a speech bubble icon.
- Exchange:** Shows a circular arrow icon.
- Settings:** Shows a gear icon.
- Help Site:** Shows a question mark icon.

At the bottom, a message reads: 'Thanks for using CommCare HQ! If you have questions, suggestions, or other thoughts, we invite you to join the discussion on the CommCare User Forums.'

[figure not shown]
Two User Roles

1. Mobile Worker

1. Logs you into the TXTXT App
2. Deploy the system and use the app
3. Register case to receive text messages

2. Web User

1. Logs you into CommCareHQ
2. Admin access to the system
3. Manage all cases and access data

[figure not shown]
Mobile Worker Task 1 of 2: Registering a case in the TXTXT App

The TXTXT App

1. Registration Form
 1. Collect essential participant information, including phone number
